5.8 Lost to Follow-Up

In the case that the subject is determined to be lost to follow-up, regulations set forth by the governing IRB/MEC (where applicable) will be followed.

5.9 Subject Follow-up after Withdrawal

Upon withdrawal from the study, no further study data will be collected or study visits will occur for the subject.

5.10 Medications

There are no medications that are required for this study. All cardiovascular medications and cardiovascular herbal treatments will be collected. The only medications that are excluded from use during this study are investigational medications.

6 STUDY DEVIATIONS

A study deviation is defined as an event within a study that did not occur according to the Clinical Investigation Plan or the Clinical Trial Agreement.

Prior approval by the Medtronic study manager is expected in situations where the investigator anticipates, contemplates, or makes a conscious decision to deviate. Prior approval is not required when a deviation is necessary to protect the life or physical wellbeing of a subject in an emergency or in unforeseen situations beyond the investigator's control (e.g. subject failure to attend scheduled follow-up visits, inadvertent loss of data due to computer malfunction, inability to perform required procedures due to subject illness, etc.).

For medically justifiable conditions which preempt a subject's ability to complete a study-required procedure, it may be permitted to complete only one deviation Case

Report Form which will apply to all visits going forward. This may also apply for other unforeseen situations (e.g. the subject permanently refuses to complete a study required procedure and the data will not contribute to the primary end point analysis, etc.). However, prior approval from Medtronic is required for such situations.

All study deviations must be reported on the Case Report Form regardless of whether medically justifiable, pre-approved by Medtronic, an inadvertent occurrence, or taken to protect the subject in an emergency. The deviation must be recorded with an explanation for the deviation and corrective/ preventative action(s).

In the event the deviation involves a failure to obtain a subject's consent, or is made to protect the life or physical wellbeing of a subject in an emergency, the deviation must be reported to the MEC/IRB (where applicable) as well as Medtronic within five (5) working days. Reporting of all other study deviations should comply with MEC/IRB policies and/or local laws and must be reported to Medtronic as soon as possible upon the center becoming aware of the deviation. Reporting of deviations must comply with IRB/ MEC policies, local laws, and or regulatory agency requirements. Refer to Investigator Reports (Table 2) for geography/country-specific deviation reporting requirements and timeframes for reporting to Medtronic and/or regulatory bodies.

Medtronic is responsible for analyzing deviations, assessing their significance, and identifying any additional corrective and/or preventive actions (e.g. amend the Clinical Investigation Plan, conduct additional training, terminate the investigation, etc.). Repetitive or serious investigator compliance issues may represent a need to initiate a corrective action plan with the investigator and site, and in some cases, necessitate freezing enrollment until the problem is resolved or ultimately terminating the investigator's participation in the study. Medtronic will provide center-specific reports to investigators summarizing information on deviations that occurred at the investigational site on a periodic basis.

7 ADVERSE EVENTS

The collection of adverse event data is not required to meet the objective(s) of this clinical trial. The products used in the clinical trial are market approved and used within the current Indications for use as indicated in the product labeling. However, it is the responsibility of the Investigator to abide by any adverse event reporting requirements stipulated by local laws and regulations and the site's Investigational Review Board (IRB) or Medical Ethics Committee (MEC).

User (Investigator) reporting of events to regulatory authorities related to market approved products may be required.

7.1 Vigilance Reporting

It is the responsibility of the investigator to report all product complaints and malfunctions immediately via the regular channels for CE marked products.

The reporting of product complaints and malfunctions of these CE-labeled devices is not part of the clinical study and should be done by the investigator.

8 SUBJECT DEATH

8.1 Data Collection

Subject deaths will be documented on the Study Exit form. The date of death and classification of cardiovascular relatedness, if known, will also be documented. It is the responsibility of the Investigator to abide by any death reporting requirements stipulated by local laws and regulations and the site's Investigational Review Board (IRB) or Medical Ethics Committee (MEC).

User (Investigator) reporting of deaths to regulatory authorities related to market approved products may be required.

9 RISK ANALYSIS

All implantable systems (pacemaker and lead(s)) utilized in this study are market released and are used according to medical, technical and ethical standards without any change to the approved use of the system. The safety and clinical performance of the market released systems have been demonstrated through previous pre-clinical testing and clinical studies in similar populations, but not necessarily the same population as this study. The risks are described in the informed consent.

The blood draw procedure that is performed as a protocol requirement is not associated with significant risk, and the procedure is carried out in many clinics as standard practice.

9.1 Potential Benefits

There are no direct benefits to the patient for participating in IMPROVE Brady. However, information gained from the study will contribute to the body of knowledge regarding diagnosis and treatment of patients with SND and may help improve the quality of care for these patients.

10 PLANNED STUDY CLOSURE, EARLY TERMINATION OF STUDY OR STUDY SUSPENSION

10.1 Planned Study Closure

Study Closure is a process initiated by distribution of an initial study closure letter. Study closure is defined as closure of a clinical study that occurs when Medtronic and/or regulatory requirements have been satisfied per the Clinical Investigation Plan and/or by a decision by Medtronic or regulatory authority, whichever occurs

first. The study closure process is complete upon distribution of the Final Report or after final payments, whichever occurs last. IRB/MEC re-approvals are required until the overall study closure process is complete.

10.2 Early Termination OR Suspension

Early Termination of the Study is the closure of a clinical study that occurs prior to meeting defined endpoints. This is possible for the whole study, a geography/country or a single center.

Study Suspension is a temporary postponement of study activities related to enrollment. This is possible for the whole study, a geography/country or a single center.

Criteria

Study Termination or Suspension

Possible reasons for considering study suspension or early termination of the study may include:

- None of the study subjects in the geography/country have been implanted with an indicated IPG at the completion of Phase I
- SND indicated subjects are \leq 5% of subjects enrolled in the geography/country and/or implanted subjects is \leq 5% of indicated subjects in the geography/country by the end of Phase I
- Enrollment is slower than anticipated
- Observed/suspected performance of the market released pacemaker from the Medtronic family of devices used in the study is different from the product's design intent.
- Decision by Medtronic or regulatory body (where the study is operating under regulatory body authority)

Investigator/Center Termination or Suspension

Possible reasons for clinical investigator or center termination or suspension include but are not limited to:

- Failure to obtain initial IRB/MEC/Head of Medical Institution approval or annual renewal of the study (where applicable)
- Consistent non-compliance to the clinical investigation (e.g. failure to adhere to inclusion/exclusion criteria, failure to follow subjects per scheduled follow-ups, etc.)
- Lack of enrollment
- Noncompliance to regulations and the terms of the Clinical Trial Agreement (e.g. failure to submit data in a timely manner, failure to follow-up on data queries and monitoring findings in a timely manner, etc.)
- IRB/MEC suspension of the center
- Fraud or fraudulent misconduct is discovered (as defined by local law and regulations)
- Investigator request (e.g. no longer able to support the study)

Procedures

If Medtronic terminates or prematurely suspends the study:

Medtronic will promptly inform the clinical investigators of the termination or suspension and the reasons and inform the regulatory authority(ies) (where required per regulatory requirements).

In the case of study termination or suspension for reasons other than a temporary IRB/MEC approval lapse, the investigator will promptly inform the IRB/MEC.

- In the case of study termination, the investigator must inform the subjects and may inform the personal physician of the subjects to ensure appropriate care and follow-up is provided.
- In the case of a study suspension, subjects already enrolled should continue to be followed out of consideration of their safety, rights and welfare.

If the investigator terminates or suspends the study without prior agreement of Medtronic:

- The investigator will promptly inform Medtronic and provide a detailed written explanation of the termination or suspension.
- The investigator will promptly inform the institution (where required per regulatory requirements).
- The investigator will promptly inform the IRB/MEC (where applicable).

If the IRB/MEC terminates or suspends its approval of the study:

- The investigator will promptly inform Medtronic and provide a detailed written explanation of the termination or suspension within 5 business days.
- Subject enrollment must stop until the IRB/MEC suspension is lifted.
- Subjects already enrolled should continue to be followed in accordance with IRB/MEC policy or its determination that an overriding safety concern or ethical issue is involved.
- The investigator will inform his/her institution (where required per local requirements).
- The investigator will promptly inform the subjects and/or the personal physician of the subjects, with the rationale for the study termination or suspension.

11 STATISTICAL METHODS AND DATA ANALYSIS

Medtronic statisticians will conduct all statistical analysis. The sample size package PASS 2008 was used for sample size evaluation. In this study, it is hypothesized that the use of a practice-specific process improvement intervention consisting of education, diagnostic algorithm(s) and documentation tools that advocate and reinforce adherence to consensus treatment guidelines will improve the quality of care for patients with sinus node dysfunction (SND). The two primary endpoints are the impact of the intervention on the diagnosis of subjects

with SND and whether SND indicated subjects receive IPG therapy. In current practice, both of these proportions are unknown for a set of patients meeting the study inclusion criteria. Three principles will guide the statistical analysis outlined below. The first principle is that the sample size calculations will use exact confidence intervals and tests to compare rates and binomial proportions. The second principle of the analysis is that sample size calculations for Phase II (intervention phase) of the study design will depend on the outcomes observed in Phase I (control phase) of the study design. Due to this, the Phase II sample size calculations provided herein are preliminary calculations that will be amended once Phase I data collection is completed. In general the study will start with a 1:2 collection ratio for Phase I and Phase II sample sizes. Twice as many subjects are enrolled in Phase II of the study design so that the study may also examine any temporal drift in the outcomes of interest or subject demographics. The 1:2 collection ratio will also allow for more information to contribute to secondary objectives 3 and 4. The third principle of the analysis is that both the statistical methods and the Phase II sample size calculations will be geography/country specific because the study outcomes are expected to vary by geography/country.

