11.1 Primary Objective(s)

Primary Objective #1

Evaluate the impact of the intervention on the diagnosis of SND.

Endpoint Definition

The absolute change in the proportion of subjects diagnosed with SND at pre-specified time points ($\% = \text{number diagnosed}/\text{number enrolled} \times 100$ at time point t where $t = 6, 12$, and any additional 6-month interval for which there is sufficient follow-up information) and the absolute change in the number of subjects diagnosed with SND per person-year.

Analysis Methods

A. Statistical Methodology

To compare the proportion of subjects with an SND diagnosis pre-intervention (Phase I) to the proportion post-intervention (Phase II), a chi-square test will determine statistical significance. The proportion of subjects diagnosed will be evaluated at multiple time points because the time to diagnosis is expected to vary by geography. Thus, times are pre-specified starting at 6 months and any additional 6-month interval thereafter for which there is sufficient follow-up data available to compare study phases. Proportions calculated at all available time points will be reported. Additionally a Poisson regression will compare the average number of subjects with an SND diagnosis in Phase I and Phase II where the subject time in study is treated as an offset in the model. The above described tests will be performed separately within geography/country as well as overall.

B. Determination of Patients/Data for Analysis

All subjects that are enrolled in the study will be included in the determination of the proportion estimates. The proportion estimates will be calculated based on information from fixed time points at 6 months of follow-up, 12 months of follow-up, and any additional 6-month interval thereafter for which there is sufficient follow-up data available to compare study phases. The number of subjects that obtain a SND diagnosis by pre-specified time point $t= 6, 12, \text{ etc.}$, is included in the numerator and the number of subjects enrolled is included in the denominator.

Sample Size Methods and Assumptions

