To compare the proportion of subjects that receive indicated therapy pre-intervention (Phase I) to the proportion post-intervention (Phase II), a Fisher's Exact test will determine statistical significance. A Fisher's exact test is recommended for smaller sample sizes. The proportion of subjects diagnosed will be evaluated at multiple time points because the time from diagnosis to implant is expected to vary by geography. Shorter time intervals will be used to evaluate the proportion of implants than for the proportion of diagnosis because implants typically occur more quickly than the SND diagnosis. Thus, times are pre-specified starting at 3 months and any additional 3-month interval thereafter for which there is sufficient follow-up data available to compare study phases. Proportions calculated at all available time points will be reported. Additionally, a Poisson regression will compare the average number of subjects with an implant where the subject time in study beginning at the time of SND diagnosis is treated as an offset in the model. The above described tests will be performed separately within geography/country as well as overall. Further, similar tests will compare the differences in the types of therapy received in Phase I and Phase II. For example, a Fisher's exact test will compare the frequency of dual chamber device use pre- and post-intervention.

B. Determination of Patients/Data for Analysis

The number of subjects that meet inclusion criteria and obtain an SND diagnosis shall be included in this analysis. The proportion estimates will be calculated based on information from fixed time points at 3 months of follow-up, 6 months of follow-up, and any additional 3-month interval thereafter for which there is sufficient follow-up data available to compare study phases. The number of subjects that obtain an IPG by pre-specified time point $t = 3, 6, \text{ etc.}$, will be included in the numerator and the number of subjects with an SND diagnosis will be included in the denominator.

Sample Size Methods and Assumptions

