The proportion of IPG therapy in SND subjects is currently unknown within the study geographies. The PANARM HF study of 2000 subjects found that 146 out of 331 bradycardia subjects (44%) had SND and that 15 (10%) of SND subjects opted for IPG therapy. PANARM HF included symptomatic HF which is different than the IMPROVE Brady population. Thus, the percentages expected in IMPROVE Brady may differ from those observed in PANARM HF. Assuming that 20% of subjects will be diagnosed with SND, this suggests that there will be 100 SND subjects in Phase I and 200 in Phase II per geography/country. Further assuming that IPG therapy will be adopted by 10% of SND subjects at three months after diagnosis, or equivalently an IPG incidence of 0.25 diagnoses per person-year, this means that the margin of error will be $\pm 8.0\%$ in a sample of 100 subjects per geography/country, based on a 95% confidence interval. If there are 100 SND subjects in Phase I and 200 SND subjects in Phase II, assuming a type I error of 0.05 and power of 0.90, a Fisher's Exact test will detect an increase in IPG therapy of at least 16% at three months after diagnosis. This means that the objective will obtain statistical significance if 52 of 200 SND subjects in Phase II

opt for IPG therapy. The Poisson regression for the same scenario has a power of 0.95 to compare IPG incidence of 0.25 versus 0.625 implants per person-year. The power of this objective will improve if the percentage of SND diagnoses is larger than 20%. In order to better account for the proportion of SND diagnosis and IPG adoption per geography/country, the Phase II sample size will be recalculated within the geography/country once Phase I data collection is complete.

Stopping Guidelines for Futility

If Phase I of the study suggests that only 5% of enrolled subjects meet an SND indication and that only 5% of those indicated opt for IPG therapy, the study may close for futility at the end of Phase I within that geography/country. Suppose that the percent of SND diagnosis is 5% and that 5% of those indicated will opt for therapy. Assuming 500 subjects in Phase I, 5,440 subjects will be needed in Phase II to see an increase in the implant rate from 5% to 30%. This suggests a scenario with insufficient power to continue into Phase II.

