1. 90% power and type I error of 0.05
2. Phase I enrolled 500 subjects with complete follow-up
3. Overall goal is 2:1 sampling for Phase II versus Phase I
4. Calculation via methods in Fleiss JL, Tytun A, Ury HK (1980): A simple approximation for calculating sample sizes for comparing independent proportions. *Biometrics* 36:343–6.

Table 2. Subjects Required to Observe Changes in SND Diagnosis

SND % Phase I	SND % Phase II	Phase II Subjects	Higher SND % Phase II	Phase II Subjects
------------------	-------------------	----------------------	--------------------------	----------------------

This document is electronically controlled. Printed copies are considered uncontrolled.

Confidential

10%	20%	N=405	25%	N=203
20%	30%	N=593	35%	N=279
30%	40%	N=717	45%	N=327
40%	50%	N=778	55%	N=347
45%	55%	N=785	60%	N=346
50%	60%	N=776	65%	N=338
60%	70%	N=711	75%	N=302
70%	80%	N=582	85%	N=237
80%	90%	N=390	95%	N=144

There is clear power to attain the first primary objective with 873 subjects or fewer in Phase II, accounting for 10% attrition.

Section 4.2 Primary objective #2 for IPG implants

Scenario 1 -- Additional assumptions:

1. No change in SND diagnosis between Phase I and Phase II, i.e., the first primary objective is not met.
2. Futility is assumed when more than 1000 subjects with complete follow-up are needed for Phase II. Areas of futility are not included in **Error! Reference source not found.** and **Error! Reference source not found..**

Table 3. For SND diagnosis rates less than 50%

	IPG % Phase I	IPG % Phase II	Phase II Subjects Needed	Accounting for Attrition	CI width for IPG % with Half of Phase II Data
10% SND = 50 SNDs	80%	95%	>1000	>1000	0.06
	85%	100%	856	952	0.03
20% SND = 100 SNDs	5%	20%	769	855	0.18
	10%	25%	1013	1126	0.17
	15%	30%	>1000	>1000	0.16

This document is electronically controlled. Printed copies are considered uncontrolled.

Confidential

	70%	85%	>1000	>1000	0.07
	75%	90%	968	1076	0.07
	80%	95%	717	797	0.06
	85%	100%	428	476	0.03
30% SND = 150 SNDs	5%	20%	513	570	0.18
	10%	25%	676	752	0.17
	15%	30%	814	905	0.16
	20%	35%	929	1033	0.16
	25%	40%	1021	1135	0.15
	30%	45%	>1000	>1000	0.15
	55%	70%	>1000	>1000	0.14
	60%	75%	1004	1116	0.14
	65%	80%	908	1009	0.13
	70%	85%	788	876	0.13
	75%	90%	645	717	0.12
	80%	95%	478	532	0.10
40% SND = 200 SNDs	85%	100%	286	318	0.08
	5%	20%	385	428	0.18
	10%	25%	507	564	0.17
	15%	30%	611	679	0.16
	20%	35%	697	775	0.16
	25%	40%	766	852	0.15
	30%	45%	817	908	0.15
	35%	50%	850	945	0.15

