	25%	40%	341	379	0.15
	30%	45%	363	404	0.15
	35%	50%	378	420	0.15
	40%	55%	385	428	0.15
	45%	60%	384	427	0.14
	50%	65%	376	418	0.14
	55%	70%	359	399	0.14
	60%	75%	335	373	0.14
	65%	80%	303	337	0.13
	70%	85%	263	293	0.13
	75%	90%	215	239	0.12
	80%	95%	160	178	0.10
	85%	100%	96	107	0.08

Additional calculations:

If the Phase II data is divided into two pieces, then there would be, ideally, an equal number of SND diagnoses and number treated with IPG in each piece. The following table describes the width of the confidence intervals around the IPG proportions estimated in Phase II, the width around the point estimate for one half of the Phase II enrollments and the width around the difference in the proportions from the two halves of Phase II.

Table 5. For SND diagnosis rates greater than 50%

IPG % Phase II	Number of SND dx in Phase II	CI width for IPG % with Half of Phase II Data	CI width for Comparison of IPG % Between Two Halves of Phase II
20%	154	0.19	0.26
25%	203	0.18	0.24
30%	245	0.17	0.23
35%	279	0.16	0.22
40%	307	0.16	0.22
45%	327	0.16	0.22
50%	340	0.16	0.21
55%	347	0.15	0.21
60%	346	0.15	0.21
65%	338	0.15	0.20
70%	323	0.15	0.20
75%	302	0.14	0.20
80%	273	0.14	0.19
85%	237	0.14	0.18
90%	194	0.13	0.16
95%	144	0.11	0.13

To compare the SND proportion between these two pieces, we have a confidence interval total width of 12% (absolute range) or less. To compare the IPG proportion between these two pieces, we have a confidence interval total width of 26% (absolute range) or less.

Futility examples

Suppose that the SND percentage is 10% and that less than 85% of those indicated will implant. Assuming 500 patients in Phase I, we will need 2,520 patients in Phase II to see an increase in the implant rate from 10% to 30%. This is an example of a scenario where we may decide not to move forward into Phase II.

This document is electronically controlled. Printed copies are considered uncontrolled.

Confidential

Suppose that the SND percentage is 5% and that 5% of those indicated will implant. Assuming 500 patients in Phase I, we will need 5,440 patients in Phase II to see an increase in the implant rate from 5% to 30%. This is another example of a scenario where we may decide not to move forward into Phase II.

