8.5.2.1. Analysis Methods

A. Statistical Methodology

To compare the proportion of subjects that receive indicated therapy pre-intervention (Phase I) to the proportion post-intervention (Phase II), a Fisher's Exact test will determine statistical significance. A Fisher's exact test is recommended for smaller sample sizes. The proportion of subjects diagnosed will be evaluated at multiple time points because the time from diagnosis to implant is expected to vary by geography. Shorter time intervals will be used to evaluate the proportion of implants than for the proportion of diagnosis because time from diagnosis to implant is typically shorter than the time from enrollment to SND diagnosis. Thus, times are pre-specified starting at 3 months and any additional 3-month interval thereafter for which there is sufficient follow-up data available to compare study phases. Proportions calculated at all available time points will be reported. Additionally, a Poisson regression will compare the average number of subjects with an implant where the subject time in study beginning at the time of SND diagnosis is treated as an offset in the model. The above described tests will be performed only for the South Asia geography as described in Section 6. Further, similar tests will compare the differences in the types of therapy received in Phase I and Phase II. For example, a Fisher's exact test will compare the frequency of dual chamber device use pre- and post-intervention.

This document is electronically controlled. Printed copies are considered uncontrolled.

Confidential

B. Determination of Patients/Data for Analysis

Subjects that meet inclusion criteria and obtain an SND diagnosis shall be included in this analysis. The proportion estimates will be calculated based on information from fixed time points at 3 months of follow-up, 6 months of follow-up, and any additional 3-month interval thereafter for which there is sufficient follow-up data available to compare study phases. The number of subjects that obtain an IPG by pre-specified time point $t = 3, 6, \text{ etc.}$, will be included in the numerator and the number of subjects with an SND diagnosis will be included in the denominator.

C. Additional Analyses

- In addition to the overall diagnosis and treatment rates between Phase I and Phase II, various descriptive summaries of the subjects will be explored by geography, including the following:

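### The implant sample sizes and futility examples come from an uncorrected normal approximation, not the exact tests the plan promises, and several fall 1 to 3 points short of 90% power under Fisher's test

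*Protocol*

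**What the plan says.** Protocol 11 sets out three principles, of which one is: "The first principle is that the sample size calculations will use exact confidence intervals and tests to compare rates and binomial proportions". SAP 8.4 has the same principle, limited to binomial proportions.

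For Primary Objective 2, Protocol 11.1 says that "a Fisher's Exact test will determine statistical significance", and SAP 8.5.2.1 keeps that test. Primary Objective 1 differs: there "a chi-square test will determine statistical significance".

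SAP 7 lists assumptions for all its calculations. They include "90% power and type I error of 0.05" and, as the method, a 1980 paper titled "A simple approximation for calculating sample sizes for comparing independent proportions". Tables 3 and 4 then give Phase II sizes for 15-point rises in implant rate, with the Phase I SND count fixed by the SND rate (20% SND is 100 subjects, and so on). More than 1,000 completing Phase II subjects counts as futile.

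The futility example in Protocol 11.1, repeated in SAP 7 and SAP 8.5.2.2, says that "5,440 subjects will be needed in Phase II to see an increase in the implant rate from 5% to 30" percent, with 5% SND. SAP 7 adds that at 10% SND "we will need 2,520 patients in Phase II to see an increase in the implant rate from 10% to 30" percent, and that at 20% SND 910 subjects suffice for 40% to 60%.

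The SAP 7 Summary claims power for a 15-point implant increase with 500 and 1,000 subjects. Protocol 11.1 and SAP 8.5.2.2 claim 16 points for Fisher's test with 100 and 200 SND subjects.

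**The concern.** The documents describe the sizing method in two ways that cannot both be true, and the method actually used does not match the planned test of a primary endpoint. Fisher's test is conservative, so a size that gives 90% power under an uncorrected approximation gives less under Fisher. The loss is greatest when one group is small, as when Phase I yields only 25 or 50 SND subjects. The figures affected are the numerical illustration of the futility guideline, the sizes from which Phase II was to be adapted, and the Summary's statement of the detectable difference.

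**Working it through.** **Inputs.** Type I error 0.05 and power 0.90 (SAP 7). Sidedness is not stated; two-sided is assumed because it reproduces the plan's figures. Phase I is 500 subjects, so Phase I SND counts are 500 × 5% = 25, 500 × 10% = 50 and 500 × 20% = 100.

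**Step 1: reproduce the futility figures.** Hold the Phase I SND count n1 fixed and find the smallest Phase II SND count n2 for which

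Φ{ [ |p2 − p1| − 1.960 √( p̄(1 − p̄)(1/n1 + 1/n2) ) ] / √( p1(1 − p1)/n1 + p2(1 − p2)/n2 ) } ≥ 0.90,

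where p̄ = (n1p1 + n2p2)/(n1 + n2) and there is no continuity correction.

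For 5% to 30% with n1 = 25 and n2 = 272:
- p̄ = (1.25 + 81.6)/297 = 0.279
- numerator: 0.25 − 1.960 × 0.0937 = 0.0663
- denominator: √(0.00190 + 0.00077) = 0.0517
- ratio 1.28, power 0.900

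Then 272/0.05 = 5,440. The same formula gives 252/0.10 = 2,520 and 182/0.20 = 910. All three match the plan exactly.

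**Step 2: reproduce the tables.** At 2:1 the same approximation gives 202.55 Phase II SND subjects for 10% to 25%, and 202.55/0.20 = 1,012.8 (Table 3: 1,013). For 75% to 90% it gives 193.41/0.20 = 967.0 (968). For 25% to 40% it gives 306.07/0.30 = 1,020.2 (1,021). For 60% to 75% it gives 301.07/0.30 = 1,003.6 (1,004). With a continuity correction the counts for 5% to 20% and 10% to 25% would be 174 and 224, not 154 and 203, and 2,520 would become 6,320.

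**Step 3: Fisher power at the stated sizes.** Full enumeration of both binomials; the two-sided p-value sums all tables no more probable than the one observed.

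| Setting | SND subjects, Phase I v II | Fisher power | Size for 0.90 |
|---|---|---|---|
| 5% to 30% (5,440) | 25 v 272 | 0.869 | first at 499 (9,980 enrolled), held from 551 (11,020) |
| 10% to 30% (2,520) | 50 v 252 | 0.880 | about 330 (3,300) |
| 40% to 60% (910) | 100 v 182 | 0.893 | about 950 to 1,090 enrolled |
| 10% to 25% (Summary, 15 points) | 100 v 200 | 0.890 | see Step 4 |
| 10% to 26% (explicit Fisher claim) | 100 v 200 | 0.923 | met |

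The ranges arise because Fisher power is saw-toothed in n. In the first setting power is 0.901 at 499, 0.897 at 500 and 0.8998 at 540. The actual type I error of Fisher's test at 25 v 272 with a common rate of 5% is 0.024. With 100 v 200, Fisher power first reaches 0.90 at a Phase II rate of 25.3%, so 16 is the smallest whole-point rise from 10% that qualifies.

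**Step 4: Tables 3 and 4 with their listed Phase I counts.** Of 119 numeric rows, 115 have Fisher power of at least 0.90. Every row at 40% SND or above has at least 0.913. The four exceptions are:

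| SND rate | Contrast | Stated size | Fisher power | Size for 0.90 |
|---|---|---|---|---|
| 20% | 10% to 25% | 1,013 | 0.894 | 218/0.20 = 1,090 (first reached) |
| 20% | 75% to 90% | 968 | 0.895 | 199/0.20 = 995 |
| 30% | 25% to 40% | 1,021 | 0.887 to 0.891 | 358/0.30, about 1,190 |
| 30% | 60% to 75% | 1,004 | 0.889 to 0.893 | 335/0.30, about 1,120 |

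The ranges for the last two rows reflect rounding the SND count down or up (306 or 307; 301 or 302).

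The pattern has a simple cause. The sizes come from a 2:1 formula, but in most rows the listed Phase I count is well above half the Phase II count, and that surplus absorbs Fisher's conservatism. In these four rows it is at or close to half (for example 100 against 101.3, and 150 against 153.0), so there is little or no surplus.

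**The case against.** The strongest reply is that SAP 7 openly names an approximation, calls the Phase II sizes preliminary, and reproduces its arithmetic correctly, so this is a wording conflict with little consequence. Much of that stands. SAP 4.1 calls the primary objectives exploratory. SAP 6 shows that the decision to continue has already been taken: only South Asia entered Phase II.

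Some stronger readings are tempting, and the documents do not support them.

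- *That 90% power is missed throughout.* The one statement that attaches 0.90 to Fisher's test, 16 points at 100 v 200, is met at 0.923. At an exact 2:1 split most table contrasts do come out just below 0.90 (0.886 to 0.899), but Tables 3 and 4 list fixed Phase I counts, and with those nearly all rows pass.
- *That the futility decision rests on a wrong number.* The 5,440 is an illustration. The criteria in Protocol 10.2 use rates of 5% or less and no sample size, and SAP 7 caps Phase II at 1,000. Both 5,440 and 11,000 are far beyond that cap. No row of Tables 3 and 4 changes side of it either: 968 becomes 995, and the other three rows already exceed it.
- *That the sizes should be kept and the test changed to mid-P or chi-square.* That would replace a pre-specified primary test after Phase I data are in, to recover a small amount of power. It is not worth doing.

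What the reply does not remove is that the first principle is untrue as written for these figures, and that the stated sizes do not give the stated power under the stated test.

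**Conclusion.** The point holds in a limited form. The implant sizes and futility examples in SAP 7 come from an uncorrected normal approximation, contrary to the first principle in Protocol 11 and SAP 8.4 and to the planned Fisher test. The shortfall from 0.90 is 3.1 points at 5,440, 2.0 at 2,520, 0.7 at 910 and 1.0 for the Summary's 15-point claim. It is about one point in the four near-cap table rows. In sample size terms the 5,440 figure is off by roughly a factor of two, because with 25 Phase I subjects power rises very slowly as Phase II grows.

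This rests on a two-sided test at 0.05 and on Phase I SND counts fixed at 500 times the SND rate. For the 15-point claim it also uses the 10% baseline that SAP 7 assumes just before its Summary. With a one-sided Fisher test at 0.025, 5% to 30% with 25 Phase I subjects did not reach 90% at any size checked (0.875 at 5,000 Phase II SND subjects). Sidedness therefore has to be stated.

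**What to change.** Recompute the futility examples and the four near-cap rows of Table 3 with Fisher's exact test at the fixed Phase I SND counts, and restate them: 5,440 as about 10,000 to 11,000 (noting that power is saw-toothed), 2,520 as about 3,300, 910 as about 950 to 1,090, and 1,013 as about 1,090, with the other three rows as in the working. Change the SAP 7 Summary from 15% to 16% for a 10% baseline, which also brings it into line with SAP 8.5.2.2. State that the tests are two-sided. Reword the first principle in Protocol 11 and SAP 8.4 to say which calculations are exact and which are approximate. Leave the primary test as Fisher's.

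The cost is a short recalculation and text edits in both documents. No patients are added, and some stated figures become slightly less favourable.
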